10.4 Causality

The investigator must attempt to explain each adverse event and its relationship to drug treatment (definite, probable, possible, probably not, definitely not). Criteria for determining the relationship of clinical adverse reactions to test drug administration are as follows:

- **Definite:** an event that follows a reasonable temporal sequence from administration of the drug or in which the drug level has been established in body fluids or tissues; that follows a known response pattern to the suspected drug; and that is confirmed by improvement on stopping the drug (dechallenge), and reappearance of the reaction on repeated exposure (rechallenge).
- **Probable:** an event that follows a reasonable temporal sequence from administration of the drug; that follows a known response pattern to the suspected drug; that is confirmed by dechallenge; and that could not be

Contains Confidential and Proprietary Information of Grifols Inc.

reasonably explained by the known characteristics of the subject's clinical state.

- **Possible:** an event that follows a reasonable temporal sequence from administration of the drug; that follows a known response pattern to the suspected drug; but that could have been produced by the subject's clinical state or other modes of therapy administered to the subject.
- **Probably not:** an event that follows a reasonable temporal sequence from administration of the drug; that does not follow a known response pattern to the suspected drug; and that could be reasonably explained by the known characteristics of the subject's clinical state.
- **Definitely not:** an event that occurs prior to the administration of study drug, is proven to be caused by the subject's disease or condition or another drug through rechallenge, or does not recur following rechallenge.

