4 STUDY DESIGN

This is a phase IV, non-randomized, multicenter study involving at least 50 evaluable subjects diagnosed with severe hemophilia A (levels of Factor VIII:C in plasma less than 0.01 IU/mL), who are male, at least six years of age and not more than 65 years of age, and with a Karnofsky Performance Score of at least 50. All subjects will have adequate immune system function (CD4 count must be greater than or equal to 400 cells/µL and subject must not have an immune system impairment or damage by disease or treatment).

Contains Confidential and Proprietary Information of Grifols Inc.

Enrolled subjects will be treated at home and with in-clinic therapy exclusively with Alphanate[®] as their sole source of FVIII concentrate for prophylaxis and treatment of all bleeding episodes and surgical procedures for a period of at least two years and a minimum of 50 exposure days, or, if 50 exposure days are not reached, for a maximum of 30 months. Alphanate[®] will be administered in accordance with the subject's usual pre-study treatment regimen. An exposure day is defined as any day on which a subject receives one or more infusions of any Factor VIII containing product. However, only one exposure day will be accrued for each surgical episode, regardless of the number of days of treatment or the number of infusions of Factor VIII associated with that surgical procedure.

A subject will continue treatment, as specified above, unless

- The subject develops inhibitors to Factor VIII at a titer greater than or equal to 5 Bethesda units (BU/mL);
- treatment with Factor VIII becomes ineffective at providing hemostasis even for a subject who has developed inhibitors with a titer of less than 5 BU/mL; or
- the subject exhibits severe or serious adverse events that prevent completion of participation in the study.

In all instances, only the inhibitor titer obtained by the central reference laboratory will be used to determine the subject's eligibility to continue his participation in the trial.

The primary endpoint of this study is:

the incidence of Factor VIII inhibitor after exposure to Alphanate[®].

The secondary endpoints are:

1. The frequency, nature, causality and severity of adverse events.
2. The occurrence of changes in biochemical parameters which would indicate alterations in renal or hepatic function.

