7.12 Treatment with Other Blood Products

Subjects will be treated for hemophilia A exclusively with Alphanate® during the course of the study. If whole blood or other blood products are used during surgery or during the control of hemorrhagic episodes, the exact dose, date and duration of treatment and prescription etiology will be entered in the appropriate case report forms.

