9.2.2 Secondary Endpoints

1. Adverse Events

The percentage of subjects experiencing one or more adverse events will be calculated. The frequency of adverse events will be reported as a proportion of the total number of infusions with Alphanate®. Causality [the proportions of adverse events judged to be definitely, probably, possibly, probably not and definitely not related to treatments with Alphanate®] and severity will be reported as percentages of the total number of adverse events occurring during the course of the clinical trial.

2. Assessment of Biochemical Tests on Serum

Descriptive statistics will be presented, with a focus on parameters which when elevated may indicate alterations in hepatic or renal function.

3. Viral Safety

Viral safety will be determined by a lack of seroconversion to reactivity against the specific blood-borne viruses for which subjects will have been tested and found to be nonreactive at the time of enrollment.

4. Consumption Analysis

Descriptive statistics will be employed to evaluate the use of Alphanate® by subjects, both for self-administration and for treatment by the investigator at the clinical site or other places of treatment.

5. Hemostasis

Descriptive statistics will be employed to evaluate the physicians' qualitative assessments of the ability of Alphanate® to control bleeding episodes when administered at the clinical site.

Contains Confidential and Proprietary Information of Grifols Inc.

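### The causality scale lets a one-off product reaction be rated 'Definitely not' related merely because later infusions were uneventful, and no rule says which category wins when two apply

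*Protocol*

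**What the plan says.** Protocol 10.4 asks the investigator to place each adverse event in one of five categories, from *Definite* to *Definitely not*. The categories that matter here are:

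- ***Definitely not*** has three alternative grounds. The first is onset before study drug. The other two read: "is proven to be caused by the subject's disease or condition or another drug through rechallenge, or does not recur following rechallenge". The grounds are joined by 'or', so the last one, that the event "does not recur following rechallenge", is enough by itself.
- ***Definite*** is where the section shows what it means by rechallenge: "reappearance of the reaction on repeated exposure (rechallenge"). Nothing asks for a deliberate or supervised re-administration.
- ***Probable*** needs reasonable timing and an event "that follows a known response pattern to the suspected drug; that is confirmed by dechallenge; and that could not be" reasonably explained by the subject's clinical state. Recurrence is not required.
- ***Possible*** needs timing and a known response pattern, "but that could have been produced by the subject's clinical state or other modes of therapy administered to the subject". Recurrence is not required here either.

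Re-exposure is built into the design. Protocol 7.12 says: "Subjects will be treated for hemophilia A exclusively with Alphanate". Protocol 4 plans at least two years of treatment and "a minimum of 50 exposure days", or up to 30 months if that number is not reached.

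The ratings feed two outputs. Protocol 9.2.2 reports "Causality [the proportions of adverse events judged to be definitely, probably, possibly, probably not and definitely not related to treatments with Alphanate", as percentages of all adverse events. SAP Table 12.4 summarizes related events, but the SAP does not say which of the five categories count as related. SAP 9.2.1 assigns the least favorable relationship when the same event occurs more than once in a subject.

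**The concern.** Failure to recur is weak evidence against a drug cause when the reaction is infrequent. Section 10.4 nevertheless gives it the same standing as onset before the first dose or proof of another cause, and attaches the strongest unrelated label. In a trial where each routine infusion counts as repeated exposure, this ground is available for most isolated reactions.

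Isolated reactions are also the kind most to be expected. Protocol 5.2 excludes patients with a history of frequent reactions to Factor VIII concentrates. Later infusions may come from a different lot (Protocol 7.9.1 has lot numbers recorded in the diary), so an uneventful one does not clear the product.

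Causality is part of the first secondary endpoint. The error can run in only one direction, because non-recurrence can move an event down the scale but never up. Two sites with identical events could also rate them at opposite ends of the scale and both be following the protocol.

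**Working it through.** The documents give no figure on this point, so there is none to reproduce. The check has a logical part and an illustrative part.

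**1. One event against the definitions.** Take a reaction that starts soon after an infusion, fits a known response pattern, resolves, and does not return at the next infusion.

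| Category in 10.4 | Met? |
|---|---|
| *Definite* | No. It needs reappearance on repeated exposure. |
| *Probable* | Yes, if resolution counts as dechallenge and the clinical state does not explain the event. |
| *Possible* | Yes, if the clinical state or other therapy could explain it. |
| *Definitely not* | Yes. It did not recur on repeated exposure. |

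The event satisfies *Definitely not* together with *Probable* or *Possible*. Section 10.4 does not say which applies. The SAP 9.2.1 rule does not settle it, because there is no second occurrence.

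**2. How often a later exposure follows.** Input: m exposure days. Assumption: a one-off reaction is equally likely on any of them. The share followed by at least one more exposure is (m − 1)/m:

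- m = 5: 4/5 = 80%
- m = 10: 9/10 = 90%
- m = 50 (the planned minimum): 49/50 = 98%
- m = 100: 99/100 = 99%

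**3. What non-recurrence shows.** Assume a reaction truly caused by the product, with recurrence risk p at each later exposure. The chance of no recurrence over k exposures is (1 − p)^k.

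| p (assumed) | next exposure, k = 1 | k = 10 |
|---|---|---|
| 0.01 | 0.99 | 0.90 |
| 0.05 | 0.95 | 0.60 |
| 0.10 | 0.90 | 0.35 |
| 0.30 | 0.70 | 0.03 |

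For infrequent reactions, non-recurrence is the expected result even when the product is the cause.

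**4. How many affected subjects could meet the criterion.** Assume a constant, independent risk q per infusion over 50 infusions. Among subjects with at least one episode, the share with exactly one is

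50q(1 − q)^49 / [1 − (1 − q)^50].

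An episode at the last infusion has no rechallenge. Given exactly one episode, it falls there with probability 1/50, so multiply by 49/50 = 0.98.

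| q (assumed) | exactly one episode | × 0.98 |
|---|---|---|
| 0.5% | 0.882 | 86% |
| 1% | 0.774 | 76% |
| 2% | 0.584 | 57% |

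The share falls as the risk rises: at q = 5% it is 0.219, and at q = 10% it is 0.029. The problem is concentrated in infrequent reactions.

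**The case against.** The strongest reply is that the text does not compel the rating. *Possible* and *Probable* do not ask for recurrence, nothing gives *Definitely not* priority, and the investigator decides. A sensible investigator would rate a well-timed, known reaction *Possible* or higher. This stands. A reader might infer that almost every one-off reaction will be classed as unrelated, but the documents support only that most such reactions meet the criterion. They contain no data on how events were rated.

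The reach is also limited. All adverse events are recorded whatever their perceived relation (Protocol 10), and serious events are reported regardless of the investigator's opinion on causality (Protocol 10.2). SAP Tables 12.2, 12.3 and 12.5 are not restricted by relationship. No decision rule uses causality, and SAP 6.4 calls the analysis primarily descriptive. This stands too, so a claim that the safety result as a whole is biased would go too far.

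Two further inferences are tempting and should not be drawn:

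- **That a viral seroconversion would always be rated unrelated and so be hidden.** Seroconversion is a separate secondary endpoint, counted without regard to causality, as is the inhibitor endpoint (Protocol 9.2.2; SAP 9.1 and 9.2). Non-recurrence also has little meaning for a persistent state.
- **That *Definite* and *Probable* are out of reach because treatment continues.** If the next routine infusion counts as rechallenge, the interval before it can equally count as dechallenge.

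The percentages in the illustration rest on assumed risks. Fifty exposure days are not exactly 50 infusions, and a subject who discontinues for a severe or serious event (Protocol 7.14) may have no later exposure.

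None of this removes the contradiction. One event can meet both a related category and the strongest unrelated one, and the plan has no rule to resolve it.

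**Conclusion.** The point holds as a defect in the wording of Protocol 10.4. Non-recurrence on repeated exposure is sufficient alone for *Definitely not*, it is available for most one-off reactions followed by another infusion, and it overlaps *Possible* and *Probable* with no precedence rule. The text permits product reactions to be rated unrelated. It does not require it.

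The possible bias favors the product and is confined to the causality percentages in Protocol 9.2.2 and to SAP Table 12.4. Its actual size cannot be derived from the documents. The illustrative 88%, 77% and 58% (about 86%, 76% and 57% after removing last-infusion episodes) assume constant, independent risks of 0.5%, 1% and 2% over 50 infusions. They show how often the criterion could be met, not how events will be rated.

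The change should be made. It is cheap, and without it the causality results cannot be read with confidence.

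**What to change.** 1. In Protocol 10.4, delete "does not recur following rechallenge" as a stand-alone ground for *Definitely not*.
2. Add that an uneventful later infusion does not by itself lower the rating.
3. Add that when an event meets two categories, the more related one applies.
4. In the SAP, state which of the five categories count as related in Table 12.4.

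A query round on events already rated *Definitely not* on this ground alone is optional. It would ask unblinded raters to revise past judgments, so any changes should be documented.

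The cost is a short wording change in the protocol (or the CRF guidance) and in the SAP. The reported percentage of related events may rise. Sample size and the primary endpoint are untouched.

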11 SUBJECT DEATHS

All deaths of subjects, regardless of cause, occurring within 24 months of the subject's entry into the protocol and which are known to the investigator will be reported in the case report on the appropriate CRF. Documentation of the subject's cause of death and a copy of the autopsy report, if any, will also be provided.

Grifols Inc. must be notified within 24 hours by telephone of all subject deaths; written follow-up must be received within 5 calendar days of initial notification.

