7.4 Every 3 Months until Month 30 and/or Off-Study

Samples for quarterly testing will be drawn \pm **10 days** of the scheduled visit date. At each of these visits, the following procedures will be performed:

1. Abbreviated physical examination including: interim medical history, vital signs (pulse, respiratory rate, oral temperature, blood pressure) and weight;
2. Factor VIII coagulant activity (Factor VIII:C);
3. Factor VIII inhibitor levels (BU/mL) in two sets of samples;
4. Hematologic status will be assessed by: complete blood count (CBC) with white blood cell (WBC) differential and platelet count.
5. Serum chemistry tests including: alanine aminotransferase (ALT), aspartic aminotransferase (AST), alkaline phosphatase (AP), lactic acid dehydrogenase (LDH), blood urea nitrogen (BUN), creatinine and total bilirubin;
6. Viral and serological tests including: testing for HBsAg, and for antibodies to HAV, HBcAb, HBsAb, HCV, HIV-1/HIV-2 (only if seronegative at baseline) and parvovirus B19 by routine immunoassay (only in subjects who are seronegative at baseline);
7. A sample of venous blood will be drawn from which approximately 5 mL of serum will be prepared and aliquoted into three vials of at least 1.5 mL of sample each. The samples will be frozen and retained at -20°C in the event that they are required for later serological or virology tests.

If at any quarterly visit, **the subject tests positive for the presence of Factor VIII inhibitors (inhibitor titer of greater than 0.6 modified BU/mL), based upon the value determined by the central reference laboratory**, the procedures specified in section 7.12 (Subjects Who Develop Inhibitors) will also be performed.

Contains Confidential and Proprietary Information of Grifols Inc.

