7.8 Miscellaneous

All enrollment tests should be performed prior to the first administration of Alphanate®. Samples drawn for quarterly testing will be drawn \pm 10 days of the scheduled visit date. The presence of inhibitors will be determined by the Nijmegen modification of the Bethesda assay (see below); the Factor VIII source for this assay will be normal pooled plasma. **Inhibitor titers will be considered valid if the subject's Factor VIII level is at or below baseline (less than 0.01 IU/mL)**, therefore, the subject should be scheduled for the quarterly visit at least three days after an infusion with Alphanate®.

If the subject's Factor VIII levels are higher than baseline at the time the plasma sample is drawn, then the subject will be rescheduled for testing within one week of the notification of the invalid result.

Assays for inhibitor to Factor VIII will be performed locally (i.e., at the coagulation testing laboratory for each clinical site) to support decisions regarding treatment. Duplicate plasma samples will be collected at each time point for confirmatory testing at a central reference laboratory. The central laboratory will utilize the Nijmegen modification of the Bethesda assay to improve reliability.¹⁷ The modification involves the following changes in reagents: (1) buffering of the normal pooled plasma used in the assay and control with 0.1 M imidazole to pH 7.4 and (2) replacing the imidazole buffer in the control mixture with immunodepleted Factor VIII-deficient plasma. In addition, to further improve the accuracy of the assays, a standardized immunodepleted plasma will be used for the performance of the assay at all clinical sites, as well as at the central reference laboratory.

The local laboratories will not be required to test for Factor VIII inhibitors using the Nijmegen modification of the Bethesda assay, but are required to provide the sponsor with a detailed description of the procedure used.

Contains Confidential and Proprietary Information of Grifols Inc.

Only the results of the assays from the central reference laboratory will be used in the determination and analysis of the primary endpoint for the clinical trial.

To determine the risk of transmission of parvovirus B19, subjects who are seronegative at enrollment will be tested approximately one week after receiving the first infusion with Alphanate[®] for the presence of parvovirus B19 by Polymerase Chain Reaction (PCR) testing.

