10.2 Serious Adverse Events

Any serious adverse event, including death, that occurs while the subject is receiving an investigational drug, irrespective of the investigator's opinion regarding drug relationship, will be reported by telephone **within 24 hours of its occurrence** to the Grifols' Personnel assigned to the study, [REDACTED], who can be contacted during working hours (8:00 a.m. to 5:00 p.m. Pacific Time) at [REDACTED] or [REDACTED] during non-working hours.

A **serious** adverse event is defined by FDA regulations in the Code of Federal Regulations (21 CFR 312.32) as any adverse event that suggests a significant hazard, contraindication, side effect or precaution. With respect to human clinical events, a serious event includes any event that results in the following outcomes: Death, a life-threatening adverse drug event, inpatient hospitalization or prolongation of existing hospitalization, a persistent or significant disability/incapacity, or a congenital anomaly/birth defect. Important medical events that may not result in death, be life-threatening, or require

Contains Confidential and Proprietary Information of Grifols Inc.

hospitalization may be considered serious adverse drug events when, based upon appropriate medical judgment, they may jeopardize the patient or subject and may require medical or surgical intervention to prevent one of the outcomes listed in the definition.

If a serious adverse event occurs, based on the investigator's judgment, appropriate therapy should be administered. Subjects will then be monitored closely as appropriate.

Oral reports of serious adverse events must be confirmed in writing within five (5) calendar days of the occurrence to Grifols Inc. and to the Institutional Review Board within their reporting guidelines.

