9.2.2 Serious Adverse Events and Death

A data listing of all Serious Adverse Events (SAEs), including treatment-emergent SAEs, will be presented. SAEs with onset prior to receiving study medication or after discontinuation of study medication will be excluded from the descriptive summaries.

A separate listing will be presented for all deaths as well as events leading to discontinuation. Complete narratives will be included for deaths.

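### Protocol section 11 requires the death form, cause-of-death documents and autopsy report only to month 24, although participation can run to month 30 and the SAP promises a listing and narratives for all deaths.

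*Protocol*

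**What the plan says.** Section 11 of the protocol has two rules on deaths.

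- **Documentation.** Deaths from any cause that are known to the investigator are entered in the case report on a CRF, with the cause documented and any autopsy report supplied. This covers deaths "occurring within 24 months of the subject's entry into the protocol".
- **Notification.** The sponsor "must be notified within 24 hours by telephone of all subject deaths", with written follow-up within 5 calendar days. This rule has no 24-month limit.

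Participation is set in protocol section 4. The floor is two years together with 50 exposure days. A longer stay is allowed "if 50 exposure days are not reached, for a maximum of 30 months". Section 8.1 repeats this for the primary endpoint, and the visit schedule in section 7.4 is headed "Every 3 Months until Month 30 and/or Off-Study".

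On the analysis side, SAP 9.2.2 states: "A separate listing will be presented for all deaths". It adds that death narratives will be complete. The listing is number 12.18 in SAP 11.1. Neither place mentions 24 months.

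**The concern.** Twenty-four months is the floor for follow-up but the ceiling for death documentation. Section 11 is the only place in the protocol that asks for the cause of death to be documented and the autopsy report supplied, so after month 24 no rule asks for either.

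The stated objective is the safety of long-term use, in about 50 subjects. Any death in such a study will be read individually, and the SAP commits the sponsor to a complete narrative for each. A narrative for a death at month 27 would have to be written without the documents that the protocol requires for a death at month 23.

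**Working it through.** The plan states no figure to reproduce. The check compares time windows and then traces each route by which a death can be recorded.

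**Windows**

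- Section 11 documentation window: 24 months from entry.
- Section 4 minimum participation: 24 months and 50 exposure days.
- Section 4 maximum if 50 exposure days are not reached: 30 months.
- Uncovered time at that maximum: 30 − 24 = 6 months, and 6/30 = 20%.
- Quarterly visits after month 24 and up to month 30: months 27 and 30, so two visits.

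The edge at month 24 is also loose. Sections 7.4 and 7.8 allow quarterly visits 10 days either side of the scheduled date, and section 11 does not say whether entry means consent, enrollment or first infusion. A subject who finishes at about two years can therefore have some study days outside the window.

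**Routes for a death after month 24**

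| Route | Death on study | Death after withdrawal, off drug, months 25 to 30 | Cause-of-death documents and autopsy report required? |
|---|---|---|---|
| Section 11, CRF and documents | No | No | Yes, but only to month 24 |
| Section 11, telephone notice and written follow-up | Yes | Yes | Not specified |
| Section 10.2, serious adverse event report | Yes, while on drug | No | Not specified |
| Sections 10 and 10.1, adverse event on CRF | Yes | Unclear (limited to events during the study) | Not specified |
| Section 7.14, discontinuation reason (tabulated under SAP 8.1) | Yes | No, already discontinued | No |
| Section 7.14, follow-up after withdrawal | Not applicable | An attempt only; no period or form given | Not specified |

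Section 10.2 drops out in the withdrawn column because it covers an event "that occurs while the subject is receiving an investigational drug".

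For a death on study, the fact of death reaches both the CRF and the sponsor. What is missing is the death entry and its supporting documents. For a subject already withdrawn, the only rule that plainly applies is the notice to the sponsor.

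**The case against.** The strongest reply is that the routes overlap. A subject who dies on study at month 27 has a fatal adverse event on the CRF, a serious adverse event report confirmed in writing within five calendar days, a discontinuation reason of death, and a separate notice with written follow-up under section 11. Section 14.1 also requires a case report for every consented subject. This reply stands, and it limits the point to documentation.

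A reader might infer that deaths after month 24 would be missing from the mortality data or from Listing 12.18. The documents do not support that. They do not name the source of Listing 12.18, which could be built from adverse event, disposition or death forms, and the SAP text covers all deaths. Omission is possible if the listing draws only on the section 11 form, but nothing says that it does.

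It is also fair to say that 20% is a ceiling for one subject. It applies in full to a subject kept to month 30 for want of 50 exposure days. The documents do not say how many subjects that will be, and they give no expected number of deaths.

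The reply does not explain why the one rule that secures cause-of-death evidence should stop at the minimum length of follow-up.

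**Conclusion.** The point holds as an inconsistency in death documentation. After month 24, and for up to 6 of 30 months, the protocol requires no death CRF entry, no documentation of cause and no autopsy report, while the SAP promises a listing and complete narratives for every death. Coverage is thinnest for a subject withdrawn and off drug who dies in months 25 to 30.

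This rests on reading section 11 literally, and on treating a death after withdrawal as not clearly falling within the study period in section 10. If sites use the death form for every death they hear of, the gap closes in practice, but the protocol does not tell them to. The primary endpoint, the sample size and the significance level are untouched. It is a small defect that is worth correcting because the correction is so cheap.

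**What to change.** In protocol section 11, replace the 24-month phrase with: *within 30 months of entry, or until the end of participation, whichever is later*. Keep the rest of the sentence.

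Both halves are needed. The fixed 30 months covers subjects who have withdrawn. The second half covers a last visit that falls after month 30. Ending the window simply at the end of participation would be a step back: a subject who withdraws at month 6 and dies at month 18 is covered now (18 < 24) and would no longer be. It would also miss withdrawn subjects who die in months 25 to 30.

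Two clarifications should go with it: define entry by a date (consent, enrollment or first infusion), and state in the SAP which forms feed Listing 12.18.

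The cost is one phrase in the protocol, one or two sentences of clarification, and a small amount of extra documentation for any late death.
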